# unique patients												
Stage I		nursing/ indep. care living						# unique patient non- episode		# unique patient episode		
incidence of an episode	month	new	old	new	old	total	dropout	cumulative patients	month	cum	month	cum
35%	1	100				100	7	100	65	65	35	35
35%	2	42	58			100	7	142	65	130	35	70
35%	3	42	58			100	7	184	65	195	35	105

	# unique patients											
Stage II		nursing/ indep. care living						# unique patient non- episode		# unique patient episode		
incidence of an episode	month	new	old	new	old	total	dropout rate	cumulative patients	month	cum	month	cum
35%	1	400		100		500	36	500	325	325	175	175
35%	2		371		93	464	33	500	302	627	162	337
35%	3		344		86	430	31	500	280	907	151	488

Therefore for this observational / exploratory study, the study design and numbers proposed (100 for the first stage and 400 for the main stage) provide reasonable assurance that a sufficient number of index events will occur in the target population.

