In **Phase 2**, a total of 500 participants will be enrolled who meet the study inclusion criteria. Any participants from **Phase 1** who want to continue to have their health measurements taken will be permitted to proceed to **Phase 2** and the remained, up to a total of 500, will be recruited from their GP surgeries and asked to participate from their own homes. Continuing care home residents will continue to receive twice-weekly visits from the project's Health Research Assistants (or care home employed

professionals, as appropriate); those participating in the study from their own homes will do so autonomously using the smartphone, the Reassure OneApp application loaded onto the smartphone, and a set of devices appropriate to their co-morbidities. They will be shown how to take their health measurements during an initial visit from one of the project's Health Research Assistants, and the Reassure OneApp application will also display reminders of how to do this. In addition to this, Health Research Assistants will be available to make visits to the participant's home to support them in collecting their health measurements at the request of the participant.

The medical devices will send back data to central server facilities in Cambridge, UK to L2S2's patient management system that will automatically adjust the visit frequency for each patient and prompt compliance to minimise dropout.

At the end of **Phase 2**, NHS activity data will be obtained from the participants' GP to allow correlation between the actual recorded instances of requirement for unscheduled care and the data collected in the trial from the medical devices.

Machine learning and statistical analysis will be used to determine the validity of using home collected and care home collected data from smart medical devices to predict future likelihood of requirements for unscheduled urgent care.

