#### 12. STATISTICS AND ANALYSIS

## 12.1. Statistical Analysis

Studies to measure interventions are designed using power calculations that minimise the risk of not finding a difference between treatments if one exists (a type II error).

In a purely observational study, such calculations are less relevant, but the study design still needs to provide assurance that sufficient data will be collected to but for this study.

This is mainly achieved by ensuring that the target population has a high event frequency of the index condition — in this case deterioration of healthcare such that hospital admission would be necessary. The mean time of residence for a patient in nursing home care is approximately 15 months, but with half the residents dying in the first six months of residence.

https://www.geripal.org/2010/08/length-of-stay-in-nursing-homes-at-end.html?m=1

Following the protocol described below, a cohort of elderly people (>65 years) living independently and in care/nursing homes, with

- a moderate or high degree of frailty,
- comorbidities as defined in the appendix using standardised NHS list
- a history of regular NHS activity will be identified.

Stage 1 of data collection will feature a universal monitoring plan across for nursing home residents and, following analysis, Stage 2 of data collection will ensure measurements are collected with frequency and using devices appropriate to the needs of different participants by tailoring the frequency and type of monitoring to the needs of the condition and patient.

To provide assurance that the sample size is likely to provide sufficient event frequency, a power calculation was performed (Jones et al. 2003).

Data provided by the West Essex CCG was used to explore different incidence rates of index episodes of health deterioration requiring NHS treatment in the target population as defined above.

As 50% of the nursing home population is likely to die within six months of admission, the recruitment of existing nursing home patients means event prevalence rates of 55% is a conservative estimate.

The lowest acceptable sensitivity of the algorithm was assumed to be 85% (SN) and the lowest acceptable specificity – 80% (SP). A confidence interval of 5% (W) was selected. The required sample size can be determined via the sensitivity or the specificity limit, depending on priorities:

$$N(SN) = \frac{TP + FN}{P} = 1.96^2 * \frac{(SN(1 - SN))}{W^2}$$

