$$N(SP) = \frac{FP + TN}{(1 - P)} = 1.96^2 * \frac{(SP(1 - SP))}{W^2}$$

		Incid	dence of h	ealth issue		
	0.3	0.35	0.4	0.45	0.5	0.55
N(SN)	653	560	490	435	392	356
N(SP)	280	301	327	356	392	435

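### Section 12.1 uses incidence as a share of participants in the sample-size grid but as a monthly rate in the Stage tables, so the precision that 500 participants give is not established

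*Protocol*

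**What the plan says.** Protocol Section 12.1 sizes the study on the precision of sensitivity (85%) and specificity (80%). On the margin it says "A confidence interval of 5% (W) was selected". The required N is the number of participants with the event divided by P, or the number without it divided by 1 − P, so P is a proportion of participants. The grid runs from 0.30 to 0.55 and states no time window. The text says that "event prevalence rates of 55% is a conservative estimate", and supports this with "As 50% of the nursing home population is likely to die within six months of admission".

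The Stage I and Stage II tables that follow carry a row label, "incidence of an episode", set at 35% in each of three months. In Stage II it gives 175 of 500, then 162 of 464, then 151 of 430. The cumulative columns stand under headings that speak of unique patients. Section 12.1 then concludes that the numbers give reasonable assurance of enough index events.

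Section 5.2 states the Stage II size: "In Phase 2, a total of 500 participants will be enrolled who meet the study inclusion criteria". Section 7.1 gives 12 weeks of participation in Phase 2, and says that Phase 1 follow-up of a participant ends when that participant exacerbates.

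**The concern.** The same word carries two units. A share of participants over an unstated period cannot be compared with a monthly rate until the rate is converted to the follow-up period, and no passage makes that conversion. The only period attached to P is the six months after admission used to argue for 55%, which is neither a month nor 12 weeks.

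What is at stake is the meaning of the reassurance. If 35% is monthly, the share of participants with an event by week 12 may lie well above the top of the grid. The event-free group then shrinks and specificity becomes the limiting measure. If 35% is the 12-week share, the projected events are far too many. In either case the reader cannot tell from Section 12.1 what precision 500 participants will deliver.

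**Working it through.** **Inputs (Section 12.1).** SN = 0.85, SP = 0.80, W = 0.05 (it acts as a half-width), z = 1.96. Stage II totals are 500, 464 and 430, with 35% a month.

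**1. The plan's own grid.**
- N(SN) = 1.96² × 0.85 × 0.15 / 0.05² / P = 195.92/P. At P = 0.35 this is 560, and the whole printed row reproduces.
- N(SP) = 1.96² × 0.80 × 0.20 / 0.05² / (1 − P) = 245.86/(1 − P). At P = 0.35 this is 378, but 301 is printed. The printed row, "N(SP) 280 301 327 356 392 435", reproduces only with 0.85 × 0.15, that is 195.92/(1 − P). This is a separate slip, so both versions are shown below.

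**2. What the cumulative columns count.** Episodes: 175 + 162 + 151 = 488. Non-episodes: 325 + 302 + 280 = 907. Sum: 1395. Patient-months: 500 + 464 + 430 = 1394. The two agree to rounding, so the columns count patient-months. Only dropouts leave in Stage II, so a person with an episode is counted again in later months.

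**3. From 35% a month to a 12-week share.** The protocol does not fix this, so several readings are set out.
- Same people every month: P = 35%.
- Stage I's own count: 105/184 = 57.1%. Stage I replaces 35 + 7 = 42 people a month, so late joiners are followed for less than three months.
- Independent months with the table's dropout: 500 × 0.35 + 464 × 0.65 × 0.35 + 430 × 0.65² × 0.35 = 344, and 344/500 = 68.8%.
- Independent months, no dropout, three full months: 1 − 0.65³ = 72.5%. With 12 weeks as 2.76 months it is 69.5%.
- In between, an assumed within-person correlation of 0.5, 0.3 or 0.1 (beta-binomial) gives 53%, 60% or 68%.

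**4. Consequences.** Half-widths are for 500 participants, in percentage points: 1.96 × √(0.1275/(500P)) for sensitivity and 1.96 × √(0.16/(500(1 − P))) for specificity.

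| Reading | P | N(SN) | N(SP), SP 0.80 | N(SP), printed row's variance | Sens. half-width | Spec. half-width |
|---|---|---|---|---|---|---|
| Same people recur, or 35% is the 12-week share | 35% | 560 | 378 | 301 | 5.3 | 4.3 |
| Correlation 0.5 (assumed) | 53% | 372 | 519 | 414 | 4.3 | 5.1 |
| Stage I count | 57% | 343 | 573 | 456 | 4.1 | 5.4 |
| Correlation 0.3 (assumed) | 60% | 326 | 617 | 492 | 4.0 | 5.6 |
| Correlation 0.1 (assumed) | 68% | 287 | 774 | 617 | 3.8 | 6.2 |
| Independent, table's dropout | 69% | 285 | 789 | 629 | 3.8 | 6.3 |
| Independent, no dropout | 73% | 270 | 895 | 713 | 3.7 | 6.7 |

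**5. Where 500 meets both targets.** N(SN) ≤ 500 needs P ≥ 195.92/500 = 39%. N(SP) ≤ 500 at SP 0.80 needs P ≤ 1 − 245.86/500 = 51%. With the printed row's variance the upper limit is 1 − 195.92/500 = 61%.

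**The case against.** A reader might infer that 35% a month simply means that 73% of participants have an event, so that 895 are needed. The documents do not support that as a fact. It needs independent months, three full months and no dropout, and the Stage II table itself has dropout. The cohort is chosen partly for repeated hospital use, so recurrence in the same people is plausible. Stage I comes nearest to the independence reading: 100 − 35 − 7 = 58 people carry over without an episode, and 35% is again applied to the full 100. But Stage I's own count ends at 57%. Like for like with the printed row, the upper figure is 713.

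A reader might also infer that 35% is the value that sized the trial. No passage says so. The grid covers a range, the text favours 55%, and at 35% the grid already asks for 560.

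The strongest defence is that the patient-month is the intended unit. Then 35% is consistent in both places, and 488 and 907 units comfortably exceed the roughly 196 and 246 needed. That reading contradicts the unique-patient headings and treats repeated months in one person as independent, so it does not rescue the text as written.

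Two points stand. Section 12.1 lets the size rest on either sensitivity or specificity, according to priorities. Its closing claim is only that enough events will occur, and at 69% to 73% that claim survives: 344 to 363 participants with an event, against 196 needed.

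**Conclusion.** The point holds as an inconsistency of unit and time window, with an assumption-dependent consequence. The Stage II projection is wrong as written, because 488 and 907 cannot both be unique patients out of 500. Read literally, 488 of 500 would be 97.6% with an episode, which the non-episode column rules out.

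If 35% is monthly and months are close to independent, sensitivity is well estimated but specificity has a half-width of about 6.3 to 6.7 points instead of 5. If 35% is the 12-week share, there are 175 participants with an event and sensitivity misses narrowly, at 5.3 points. Neither 35% nor 69% to 73% lies in the 39% to 51% band where 500 meets both targets. The 55% in the text is also just outside it, with N(SP) = 245.86/0.45 = 546.

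These figures assume SP = 0.80, W as a half-width and one classification per participant over 12 weeks. The 73% is the upper end when months are independent or episodes tend to recur in the same people. The synopsis gives a 24-week participation period, which may span both phases; I used the 12 weeks of Section 7.1, which match the three-month tables. None of this shows that the study must be larger.

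**What to change.** In Section 12.1:

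- Define P as the share of participants with at least one index event in the 12-week window. Derive it from the West Essex CCG data for a window of that length.
- Use that P in both the formula and the Stage tables.
- Relabel the cumulative columns as patient-months, or count each person once.
- Extend the grid to about 0.75 to cover the plausible range, computing the specificity row with the stated 80%.
- Restate the sensitivity and specificity half-widths that 500 participants give, as a range over the plausible P.

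The cost is a recalculation and revised tables. Enrolment does not change. The downside is that the stated precision becomes less favourable.

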### 12.2. Decision points

An interim report will be presented to the CCG based on the data collected from the first 100 patients in the care homes in the middle of May 2020. This will include outcome performance measures on the device / condition groupings, the confidence of correlation between the measurements and the actual data from the A&E departments and the GPs. The decision when to proceed to phase 2 will be made jointly by L2S2 and the CCG.

### 12.3. Stopping rules

The CCG has the final decision to end the trial. This is a non-interventional, observational study and the data will not be analysed until the study is complete, and therefore other than the CCG deciding that the study is not being managed correctly, the study will proceed to the planned end.

## 12.4. Procedure for Accounting for Missing, Unused, and Spurious Data.

All data collected will be validated to ensure values are in bounds before inclusion in aggregated datasets. Otherwise all data collected will be included.

#### 12.5. Service transformation recommendations

Phases 1 and 2 of this study are focused on establishing whether reliable predictions of future health exacerbations that would result in the requirement for urgent unscheduled care can be correlated to measurements derived from medical devices used by patients at home. Whilst a full health economics analysis is not a requirement of this investigation, accurate cost data will be measured and passed through to the CCG for further analysis after the study is complete. The CCG will have access to detailed historical cost data.

A final output of this study will be service transformation suggestions. These will be prepared by L2S2 with assistance from the CCG. L2S2 will seek advice from contracted A&E specialists and GPs.

#### 13. DATA MANAGEMENT

All data on L2S2's servers are encrypted AES 256 and are only available in the physically secure server room.

#### 13.1. Source Data

Participants' NHS activity data and relevant data related to their health condition(s) will be collected with their consent from their GPs' clinical systems and direct from participants using a personal app — Reassure OneApp — installed on the smartphone loaned to them for the duration of the study. Data gathered by the carers will be entered and stored in an L2S2 electronic system (in wide use within the NHS — ISO 27001 / ISO 13485 accredited / DS&P Toolkit accredited / Cyber Essentials) whilst in the presence of the participants. All documents will be stored safely in confidential conditions. On all study-specific documents containing data, other than the signed consent, the participant will be referred to by the study participant number/code, not by name.

## 13.2. Access to Data

Direct access to anonymous data will be granted to authorised representatives from the Sponsor and host institution for monitoring and/or audit of the study to ensure compliance with regulations.

## 13.3. Data Recording and Record Keeping

All trial data will be entered directly into the L2S2 record system. This system is validated and is used in accordance with the company's ISO 27001 and ISO 13485 procedures.

The participants will be identified by a unique trial specific number and/or code in any database. The name and any other identifying detail will NOT be included in any trial data electronic file.

The study data will be stored in L2S2 servers at [name], Cambridge and encrypted backups will be stored at L2S2's approved secondary site in Cambridge. Both sites are approved for the storage of identifiable data (NHS Digital) and are accredited to ISO 27001 and Cyber Essentials.

The identifiable data will be destroyed when the final outcome reports are created. The consent form will be retained while ever data is held.

#### 14. QUALITY ASSURANCE PROCEDURES

The L2S2 Reassure system enforces procedures and maintains a full audit of all activity. The study will be managed to ISO 9001 and ISO 13485 procedures. Standard operating procedures will be created for all aspects of the study. L2S2 will be audited for compliance to both standards by BSI during the study period.

In addition, the quality assurance procedures will include a risk adaptive approach based on a formal risk assessment, planned monitoring activities and the involvement of a number of study oversight personnel.

#### **15. RISK ASSESSMENT**

A risk assessment and monitoring plan will be prepared before the study opens and will be reviewed as necessary over the course of the study to reflect significant changes to the protocol or outcomes of monitoring activities.

#### 16. STUDY MONITORING

Regular monitoring will be performed according to the study specific Monitoring Plan. Data will be evaluated for compliance with the protocol and accuracy in relation to source documents as these are defined in the study specific Monitoring Plan. Following written standard operating procedures, the monitors will verify that the clinical study is conducted and data are generated, documented and reported in compliance with the protocol, GCP and the applicable regulatory requirements.

## **17. PROTOCOL DEVIATIONS**

A study related deviation is a departure from the ethically approved study protocol or other study document or process (e.g. consent process or administration of study intervention) or from Good Clinical Practice (GCP) or any applicable regulatory requirements. Any deviations from the protocol will be documented in a protocol deviation form and filed in the study master file.

A standard operating procedure is in place that describes the procedure for identifying non-compliances, escalation to the central team and assessment of whether a non-compliance /deviation may be a potential Serious Breach.

#### **18. SERIOUS BREACHES**

A "serious breach" is a breach of the protocol or of the conditions or principles of Good Clinical Practice which is likely to affect to a significant degree –

- (a) the safety or physical or mental integrity of the trial subjects; or
- (b) the scientific value of the research.

In the event that a serious breach is suspected the Sponsor must be contacted within 1 working day. In collaboration with the clinical investigator, the serious breach will be reviewed by the Sponsor and, if appropriate, the Sponsor will report it to the approving REC committee and the relevant NHS host organisation within seven calendar days.

#### 19. ETHICAL AND REGULATORY CONSIDERATIONS

#### 19.1. Declaration of Helsinki

The Investigator will ensure that this study is conducted in accordance with the principles of the Declaration of Helsinki.

#### 19.2. Guidelines for Good Clinical Practice

The Investigator will ensure that this study is conducted in accordance with relevant regulations and with Good Clinical Practice.

#### 19.3. Approvals

Following Sponsor approval, the protocol, informed consent form and participant information sheet will be submitted to an appropriate Research Ethics Committee (REC), and HRAand host institutions for written approval.

The Investigator will submit and, where necessary, obtain approval from the above parties for all substantial amendments to the original approved documents.

### 19.4. Other Ethical Considerations

No children will be included in this study. This study is non-interventional and data will not be analysed until the interim report and final report stages.

In the unlikely event that one of the study professional HCAs observes a severe worsening of condition in a participant that is not known to the participant's medical team and such 10that the abnormality was medically important, they will discuss the implications with the participant's care team. Participants will not be informed. It is important to note that remote monitoring data are not collected for diagnostic purposes, and therefore the monitoring is not a substitute for a clinical appointment. Rather, the monitoring is intended for research purposes only.

## 19.5. Reporting

The CI shall submit once a year throughout the study, or on request, an Annual Progress report to the REC Committee, HRA (where required) host organisation, Sponsor and funder (where required). In addition, an End of Study notification and final report will be submitted to the same parties.

## 19.6. Participant Confidentiality

The study will comply with the General Data Protection Regulation (GDPR) and Data Protection Act 2018, which require data to be de-identified as soon as it is practical to do so. The processing of the personal data of participants will be minimised by making use of a unique participant study number only on all data collected in study databases. Personal identifiable data will be kept separate from the study data and only used by the carers who attend the participants and for keys to correlate with hospital and GP databases. All documents will be stored securely and only accessible by study staff and authorised personnel. The study staff will safeguard the privacy of participants' personal data.

## 19.7. Expenses and Benefits

No payments will be made to study participants.

#### 20. FINANCE AND INSURANCE

## 20.1. Funding

This trial is funded by NHS England, though funding has been disbursed to NHS West Essex Clinical Commissioning Group who have contracted the running of the trial to L2S2 Ltd and act as the Commissioning Authority.

#### 20.2. Insurance

This is an NHS sponsored project so the NHS Indemnity Scheme shall apply.

L2S2 carries professional indemnity insurance (£10 million) and public liability insurance (£5 million).

## 20.3. Contractual arrangements

Appropriate contractual arrangements will be put in place with all third parties, including but not limited to: hospitals providing baseline and monthly data, GP surgeries providing baseline and monthly data, contract care organisations, any subcontractors.

#### 21. PUBLICATION POLICY

The Investigators will be involved in reviewing drafts of the manuscripts, abstracts, press releases and any other publications arising from the study. Authors will acknowledge that the study was funded by West Essex CCG. The West Essex CCG will own study data and will control press releases. Authorship will be determined in accordance with the ICMJE guidelines and other contributors will be acknowledged.

